8.1.3. Statistical Methods for Time_to_Event Variables

For time to event variables such as time to achieve NRS response, Kaplan-Meier analyses will be used to account for any right censoring, i.e., event not observed. Kaplan-Meier survival estimates and the number and percentage of subjects experiencing the relevant event or being censored will be summarized and plotted by treatment group. 90% CIs will be generated for the estimate of time to NRS response.

8.2. Statistical Analyses

8.2.1. Standard Analyses

Study conduct and subject disposition

The number of subjects randomized, treated, completing and discontinuing from the study, as well as the number of subjects in each analysis population will be summarized by treatment group. For subjects who did not complete the study, the reasons for withdrawal from the study will be presented.

Demography and baseline characteristics

Demographic and baseline characteristics will be summarized by randomized treatment group for all randomized and treated subjects. Continuous variables will be summarized using mean and standard deviation. Categorical variables will be summarized using relative frequency. Key demographic and baseline variables to be summarized include: geographic region, age, gender, race, ethnicity, height, weight, body mass index, disease duration, baseline EASI score, baseline IGA, baseline NRS score etc.

Exposure and compliance

Exposure to the study therapy is defined as the number of days the subject is known to be on study drug. The exposure is roughly calculated as the date of the last visit (including the follow up visits) of the subject in this study minus the date of the first administration of the study therapy plus one. Summary statistics will be provided for exposure by treatment group.

For each subject, percent will then be calculated using the following formula:

$$\text{Percent Compliance} = \# \text{ doses actually administrated} / \# \text{ doses planned} * 100\%.$$

The number of doses planned or actually administrated is counted up to the conclusion date of the treatment period. Summary statistics will be provided to percent compliance by treatment group.

Descriptive Statistics

090177e18dabc776\0.1\Draft\Versioned On:07-Feb-2018 10:11 (GMT)

Descriptive statistics for all primary, secondary and exploratory endpoints presented in [Section 6](#) will be tabulated.

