- n. Subjects should take the medication from study Days 1 to 85. Subjects will be encouraged to take the medication after breakfast whenever it is possible. However, at study visit days, subjects are to be instructed to refrain from dosing at home, and are to take the dose in the clinic.
- o. Non-medicated study emollient and sunscreen will be provided to subjects at the Screening visit and re-supplied during the study as applicable. Subjects will start the study provided emollient 7 days prior to Day 1 through to the End of Study visit.
- p. For subjects at a selected study site(s), photographs of treatment-eligible atopic dermatitis will be obtained at Day 1 and Week 6. Areas photographed should be recorded in study documents so that the same atopic dermatitis body region(s) will be photographed at Week 6. Additional photographs may also be taken at Week 8 and/or Week 12 at the investigator's discretion.
- q. Pruritus Numerical Rating Scale (NRS) will be assessed daily from Day 1 to 15 and then at study site at every study visits.

r. CCI [REDACTED]

090177e18dabc380\0.1\Draft\Versioned On:07-Feb-2018 09:59 (GMT)

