6.3.2. Visit 10, Day 99/Week 14 (± 3 day)

- Conduct targeted physical examination.
- Obtain vital signs including pulse rate, blood pressure, respiratory rate (after at least 5 minutes of rest) and oral or tympanic temperature.
- Obtain samples for laboratory testing: blood chemistry, hematology and urine pregnancy test (female subjects of childbearing potential only).

- Conduct clinical evaluations including IGA, EASI, BSA, and SCORAD.
- Administer PROs including Pruritus NRS, PtGA, DLQI, POEM, and HADS.
- Review **CCI** (in selected country/ies) as necessary.
- Confirm proper contraception is being used.
- Review any changes in the subject's concomitant treatments information.
- Assess for occurrence of Adverse Events by spontaneous reporting of adverse events and by asking the subjects to respond to a non-leading question such as "How do you feel?"

6.3.3. Visit 11, End of Study Visit, Day 113/Week 16 (±3 day) or Early Termination Visit

The following procedures will be completed:

- Conduct complete physical examination.
- Obtain vital signs including pulse rate, blood pressure, respiratory rate (after at least 5 minutes of rest) and oral or tympanic temperature.
- Obtain weight.
- Perform single 12-lead ECG.
- Obtain **fasting** samples for blood chemistry including lipid profile.
- Obtain samples for laboratory testing: hematology, urinalysis, urine pregnancy test (female subjects of childbearing potential only), EBV, CMV, HSV1, HSV2, VZV, IgE, hsCRP, IP-10, IL-31, CCL17, TBNK, T cell subsets, and exploratory biomarker samples.
- Conduct clinical evaluations including IGA, EASI, BSA, and SCORAD.
- Administer PROs including Pruritus NRS, PtGA, DLQI, POEM, and HADS.
- Review **CCI** (in selected country/ies) as necessary.
- Confirm proper contraception is being used.
- Review any changes in the subject's concomitant treatments information.
- If early termination visit, perform drug accountability procedures.

- Assess for occurrence of Adverse Events by spontaneous reporting of adverse events and by asking the subjects to respond to a non-leading question such as “How do you feel?”

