5.2. Safety Analysis Set

The safety analysis set (SAS) will be all subjects who receive at least 1 dose of investigational product. The safety analysis set will include the follow-up period. The safety analysis set excluding follow-up period data may be conducted as a sensitivity analysis.

The final safety database will include all reported safety data at the time of database release.

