7.4. Safety Endpoints

Missing data for safety endpoints will not be imputed and will be left as missing. The follow-up period will be included for the safety endpoint. A sensitivity analysis maybe carried out excluding the follow-up period.

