8.1.1.3. Safety Data

An unconditional exact method for risk difference proposed by Chan and Zhang (1999) will be used to compare each active dose to placebo. P-values and 90% confidence intervals will be formed for tier 1 events and 90% confidence intervals will be formed for tier 2 events.

The exposure adjusted summaries for the Tier 1 and Tier 2 events will also be conducted. See [Section 8.2.1](#) for the calculation of exposure.

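### SAP 8.2.1 defines exposure as days on study drug but counts to the last follow-up visit, so a completer is tabulated with 113 days instead of 85 (+33%)

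*SAP*

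**What the plan says.** The exposure paragraph of SAP 8.2.1 opens with a definition: "Exposure to the study therapy is defined as the number of days the subject is known to be on study drug". The next sentence gives the rule: "The exposure is roughly calculated as the date of the last visit (including the follow up visits) of the subject in this study", from which the date of first administration is subtracted and one is added. The result is to be summarised by treatment group. For compliance, the same section stops earlier: "The number of doses planned or actually administrated is counted up to the conclusion date of the treatment period".

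SAP 8.1.1.3 uses the result again: "The exposure adjusted summaries for the Tier 1 and Tier 2 events will also be conducted". It points the reader to 8.2.1 for how exposure is calculated, and SAP 8.2.3 repeats the commitment.

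On which events count, SAP 5.2 says "The safety analysis set will include the follow-up period" and SAP 7.4 says "The follow-up period will be included for the safety endpoint". Both sections allow an optional sensitivity analysis without follow-up. Protocol 8.2 records adverse events from the first dose to the subject's last visit. Protocol 9.3 lists on-treatment adverse events among the safety endpoints.

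On timing, note n to the protocol's Schedule of Activities says "Subjects should take the medication from study Days 1 to 85", and the heading of protocol 6.3.3 reads "Visit 11, End of Study Visit, Day 113/Week 16".

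**The concern.** The definition and the rule are consecutive sentences and describe different quantities. No study drug is taken in follow-up: the last dose is given in clinic at Week 12 and none is dispensed at that visit. The rule therefore adds the whole off-drug follow-up to every completer's days on drug, always upward.

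Two outputs are affected. The exposure table would show more drug days than the trial gives, in every arm. The exposure-adjusted adverse event summaries would carry a denominator that is not exposure. The distortion also varies between subjects, because it depends on when drug was stopped and how much follow-up was attended. It cannot be divided out by a constant.

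**Working it through.** **Inputs**

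- First dose: Day 1. Last dose for a completer: Day 85 (Schedule of Activities, note n), taken at the Week 12 visit, window ±3 days, so Days 82 to 88 (protocol 6.2.7).
- Last visit: Day 113, window ±3 days, so Days 110 to 116 (protocol 6.3.3).
- Planned dropout: 20% (protocol 9.1, SAP 4.2.4).
- After stopping drug early, the first follow-up visit is 1 week after the last dose (protocol 6.4).
- Assumed, because the documents do not give them: the day of stopping, the length of follow-up attended after stopping, and the ratio of off-drug to on-drug event rates.

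The SAP states no exposure total, so there is no figure to reproduce. The exposure rule is the same formula as the relative-day rule in SAP Appendix 1, so a last visit on Day 113 gives exactly 113.

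**Completer**

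- SAP rule: 113 − 1 + 1 = 113 days.
- Days on drug: 85 − 1 + 1 = 85 days.
- Ratio: 113/85 = 1.329, an excess of 28 days or 32.9%.
- Extremes of the windows: 110/88 = 1.25 and 116/82 = 1.415.

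**Early stopper** with last dose on day L and f days of follow-up: ratio = (L + f)/L

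| L | f | Ratio |
|---|---|---|
| any | 0 | 1.00 |
| 28 | 7 | 1.25 |
| 28 | 28 | 2.00 |
| 43 | 28 | 1.65 |
| 8 | 28 | 4.50 |

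**Arm mean**, 20% stopping on day L and 80% completing: (0.8 × 113 + 0.2 × (L + f)) / (0.8 × 85 + 0.2 × L)

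| L | f = 0 | f = 28 |
|---|---|---|
| 15 | 1.315 | 1.394 |
| 43 | 1.292 | 1.366 |
| 71 | 1.273 | 1.341 |

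Over these assumptions the arm mean is overstated by a factor of 1.27 to 1.39.

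**Adverse event rate for a completer.** Let r be the off-drug event rate divided by the on-drug rate, with events counted at a constant rate within each period. The planned rate relative to the true on-drug rate is (85 + 28r)/113:

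- r = 0, or follow-up events not counted: 85/113 = 0.75
- r = 0.5: 99/113 = 0.88
- r = 1: 113/113 = 1.00

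**Changing only the denominator to 85 days** while still counting follow-up events gives (85 + 28r)/85:

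- r = 0.5: 99/85 = 1.165
- r = 1: 113/85 = 1.329

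**The case against.** The strongest defence is that the denominator suits its main downstream use. Follow-up events are in the safety set and are recorded to the last visit, so first dose to last visit is the matching time at risk. This stands: as planned, the exposure-adjusted summaries can be read as valid on-study rates, and the fault there is the name. It does not rescue the exposure table, where the same number is presented as days on drug.

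The rule is also openly described as rough and written out in full. That does not excuse it. A rough rule would miss by a few days in either direction, whereas this one adds four weeks to every completer, and neither document gives an exposure based on last dose.

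Several limits on the size do stand:

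- The analysis without follow-up is optional, and nothing says the exposure-adjusted summaries would be repeated in it with an unchanged denominator. The factor of 0.75 from leaving out follow-up events is therefore conditional.
- The SAP does not say whether these summaries count events or subjects, or whether time stops at the first event. The rate factors above assume event counts over the full period and would not carry over to first-event rates.
- The early-stopper and arm-mean figures are illustrations on assumed stopping days. The 4.5-fold case is an extreme outside the Day 15 to 71 range used for the arm mean.
- Percent compliance does not use the exposure figure and is not affected. The dose-count rule matters only because it shows that the section uses two different end dates.
- Last dose minus first dose plus one still includes any days of interrupted dosing, which protocol 5.3 anticipates. Strictly, it is treatment duration. This is a smaller gap than the one being closed.

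**Conclusion.** The concern holds. Followed as written, the SAP produces an exposure table that overstates days on drug by 28 days, or 33%, for a completer at target days. That figure comes from the documents alone. The arm-mean overstatement of 27% to 39% rests on the planned 20% dropout and assumed stopping between Day 15 and Day 71 with 0 to 28 days of follow-up.

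The exposure-adjusted Tier 1 and Tier 2 summaries are mislabelled. They understate the on-drug event rate only if events are rarer off drug or follow-up events are left out. The documents support no statement about the direction of any distortion between arms.

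The primary efficacy analysis and the main Tier 1 and Tier 2 proportions and risk differences do not depend on this quantity. It should be corrected before the tables are produced, but it does not threaten the trial's main conclusions.

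**What to change.** In SAP 8.2.1, calculate exposure as last dose date minus first dose date plus one. State whether interruption days are included, and if they are, call the result treatment duration.

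In SAP 8.1.1.3 and 8.2.3, choose one matched pair for the adverse event rates and name it:

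- on-treatment events over days on drug, with any post-dose risk window applied to both events and time; or
- all events including follow-up over first dose to last visit, labelled as time on study.

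State also whether the summaries count events or subjects, and whether time is cut at the first event. Do not shorten the denominator while keeping follow-up events. For a completer that would overstate the rate by 16% if the off-drug rate is half the on-drug rate, and by 33% if the two are equal.

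The core correction costs one SAP definition, one derivation and a table label. The last dose date is already needed to time the first follow-up visit after early stopping (protocol 6.4). The sponsor should confirm that it is captured on the CRF.

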8.2.2. Statistical Analyses for Efficacy, Health Outcomes and Biomarkers

Unless stated otherwise, the analyses for efficacy, health outcomes and biomarkers will be based on the FAS population, as defined in [Section 5.1](#). A summary table of the analysis strategy for all the efficacy and health outcome is shown in [Section 8.2.5](#).

8.2.2.1. Analysis for the Primary Endpoint

The primary efficacy endpoint is the IGA response at Week 12. The primary analysis data will be based on FAS population with NR as missing value imputation method. Baseline is defined as the score for each assessment prior to the first dosing. .

The objective for the analysis of primary endpoint is to characterize the dose response in inducing clinical IGA reduction in subjects with moderate to severe atopic dermatitis. To achieve this objective, a three parameter Emax dose response model specified in [Section 8.1.1.1](#) will be used as the primary analysis approach to characterize the dose response relationship.

As sensitivity analyses, GLMM will be employed on IGA response from all visits including follow-up. These analyses will be carried out on the FAS population with OC as described in [Section 8.1.1.1](#). P-values and 90% confidence intervals for odds ratios between treatments and placebo will be computed at each visit. Logistic regression will be performed at each visit on FAS with NR as additional sensitivity analysis.

8.2.2.2. Analyses for the Secondary Endpoints

8.2.2.2.1. Analysis of continuous secondary endpoints

All primary analyses for the continuous secondary endpoints are based on the FAS population with OC. Baseline is defined as the score for each assessment prior to the first dosing. These endpoints include:

- *Percent change from baseline in the EASI total score at all scheduled time points*
- *Percent change from baseline in the pruritus NRS at all scheduled time points*
- *Change from baseline in affected body surface area (BSA) at all scheduled time points*
- *Change from baseline in SCORing atopic dermatitis (SCORAD) at all scheduled time points*
- Percent change from baseline in SCORing atopic dermatitis (SCORAD) at all scheduled time points

All continuous secondary endpoints including all time points will be analyzed using MMRM as described in [Section 8.1.2](#). LS means at each time point will be computed. P values and

90% confidence intervals will also be computed for placebo adjusted effect (LS mean difference between treatment and placebo) at each time point. Sensitivity analysis will be performed using ANCOVA on FAS with LOCF imputation as described in [Section 8.1.2](#).

Dose response analysis on the percent change from baseline in the EASI total score at Week 12 will be performed using a 3-parameter Emax model as described in [Section 8.1.2](#).

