1.5. Summary of PF-04965842 Pharmacokinetics

PF-04965842 was rapidly absorbed following single dose oral solution/suspension administration over the dose range 3 mg to 200 mg with time to maximum absorption (T_{max}) ranging between 0.55 to 0.77 hours. Median T_{max} at doses of 400 mg and 800 mg were 1.5 and 3.9 hours, respectively, which indicated the slower absorption compared to lower doses. PF-04965842 showed a monophasic decline at dose <100 mg with biphasic profiles at doses \geq 100 mg. C_{max} following the single-dose administration generally increased in proportion to the dose from 3 mg to 800 mg. In contrast, both area under the plasma concentration-time curve from time zero extrapolated to infinity (AUC_{inf}) and area under the plasma concentration time profile from time zero to the last quantifiable concentration (AUC_{last}) were dose proportional in the range of 3 mg to 200 mg, while a greater than proportional increase was observed at doses of 400 and 800 mg. The arithmetic mean terminal phase half-life ($t_{1/2}$) was 1.9 to 4.9 hours.

Following QD administration over the dose range 30 mg to 400 mg and 100 mg and 200 mg BID for 10 days, median T_{max} ranged between 0.50 to 0.77 hours. After attainment of C_{max} , the disposition of PF-04965842 was consistent with that observed following single-dose administration, showing a biphasic decline following all but the lowest dose and an arithmetic mean terminal phase $t_{1/2}$ between 2.8 to 5.0 hours. Although C_{max} generally increased in proportion to the dose up to 100 mg BID, it increased more than the dose increased at 400 mg QD and 200 mg BID. The same trend was also observed for area under the plasma concentration-time curve (AUC_{tau}) over the dosing interval ($\tau = 12$ or 24 hours). The observed accumulation ratio (R_{ac}) following 200 mg BID was 2.0 and 2.5 for AUC_{tau} and C_{max} , respectively. R_{ac} was 1.1 to 1.5 at other doses. Therefore, the results showed that drug concentration accumulation is minimal after repeated oral administration at lower doses,

consistent with the prediction from $t_{1/2}$. Urinary recovery of PF-04965842 was low, with <5% of the dose recovered unchanged in urine across all doses and regimens in all cohorts.

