9.2.2. Analysis of the Secondary Endpoints

The key secondary endpoint is the percent change from baseline in EASI score at Week 12. The treatment effect in each of the active treatment groups is the difference (mean percent change from baseline at Week 12 in the active treatment group minus the mean percent change from baseline at Week 12 in the placebo group) in the mean percent change from baseline of a EASI score at Week 12.

The estimates for treatment effect will be obtained by fitting the mixed-effect models repeated measures (MMRM) assuming missing at random to the percent change of EASI score from baseline score if there is no convergence issue. The model will include time, treatment (active doses and placebo), treatment by time interaction as fixed effects and baseline value as a covariate. We will allow an unstructured variance-covariance matrix. Covariance matrices with other structure will be considered in sensitivity analysis. Estimates and the appropriate confidence intervals will be presented.

In addition to the primary analysis based on the pairwise evaluation of the treatment effects, we will explore the modeling of dose-response relationship for the key secondary endpoint.

MMRM will also be employed for other continuous endpoints such as percent change from baseline in the EASI total score at all scheduled time points, percent change from baseline in the pruritus NRS from baseline at all scheduled time points, change from baseline in affected BSA at all scheduled time points, and change from baseline in SCORAD at all scheduled time points. Estimates of mean values and the mean differences from placebo at each week

(along with 90% confidence intervals) will be reported. Descriptive statistics of the actual and change from baseline values will be calculated.

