7.1. Efficacy Data

[figure not shown]
For the binary efficacy data such as IGA response, subjects who receive at least one investigational product and discontinue from the study before Week 12 will be considered as non-responders (NR) for all subsequent visits during the treatment phase until Week 12.

For the continuous efficacy endpoints such as percent change from baseline in EASI score at Week 12, the observed case (OC) approach and the last efficacy observation carrying forward (LOCF) missing value imputation will both be considered. The efficacy endpoints will be set to missing after rescue treatment is used. The LOCF method will then be used to impute missing values.

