8.1.2. Statistical Methods for Continuous Variables

Unless stated otherwise, descriptive summary statistics for continuous variables will be presented on FAS with OC by treatment group and will include the following: n, mean, median, standard deviation, minimum and maximum. In addition, similar tables will be generated on FAS with LOCF imputation for EASI, NRS, SCORAD scores and BSA. For longitudinal continuous variables, such as the percent changes from baseline of EASI score, percent changes from baseline of pruritus NRS score etc., the primary analysis will be conducted using a mixed model repeated measures (MMRM) analysis on FAS with OC. Each analysis will be performed with a restricted maximum likelihood (REML) MMRM analysis. The model will include treatment and visit as fixed factors, along with the interaction of treatment and visit. Baseline measurement such as baseline disease severity will be used as a covariate. An unstructured covariance structure will be used to model the within-subject variability. In the event there are difficulties with initially fitting an unstructured covariance matrix, a variety of methods will be used to facilitate the computations. The Kenward-Roger approximation will be used to estimate the denominator degrees of freedom. The model will be fit using SAS PROC MIXED. Least squares (LS) means of the treatment groups at each available visit along with 90% CIs will be presented. LS mean difference between treatment and placebo for each visit will be presented along with 90% confidence intervals. Least squares means and confidence intervals will be back transformed to an appropriate scale when necessary. In addition, ANCOVA including treatment and baseline disease severity on FAS with LOCF imputation will be performed.

For the key secondary endpoint (percent change of EASI score from baseline to Week 12), a dose-response relationship will be characterized by a three-parameter Emax model described in Section 8.1.1.1, in which case E denotes the percent change of EASI at Week12 and E₀ denotes the percent change of EASI at Week12 in placebo group.

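### LOCF is the only check on missing at random for Week 12 percent change in EASI, and agreement with it would not show that the result is robust

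*SAP*

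**What the plan says.** For percent change in EASI, SAP 8.1.2 states that "the primary analysis will be conducted using a mixed model repeated measures (MMRM) analysis on FAS with OC". Protocol 9.2.2 describes the same model as "mixed-effect models repeated measures (MMRM) assuming missing at random".

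The departure from that assumption is in SAP 8.2.2.2.1: "Sensitivity analysis will be performed using ANCOVA on FAS with LOCF imputation as described in" Section 8.1.2. That section reads: "In addition, ANCOVA including treatment and baseline disease severity on FAS with LOCF imputation will be performed". SAP 7.1 sets efficacy values after rescue to missing and adds: "The LOCF method will then be used to impute missing values".

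No other planned item varies the missing-data assumption for this endpoint:
- Protocol 9.2.2 says "Covariance matrices with other structure will be considered in sensitivity analysis", which stays within missing at random.
- The SAP 8.2.5 table marks absolute change in EASI, by MMRM on observed cases, as a sensitivity approach. That changes the scale only. The table does not list the LOCF ANCOVA.
- SAP 8.1.1 plans non-responder tables for EASI50/75/90. These summarise different, binary endpoints.
- The Emax model for EASI at Week 12 (SAP 8.1.2) comes with no missing-data rule.

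No reference-based, delta-adjusted or tipping-point analysis is planned.

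**The concern.** A missing-data sensitivity analysis should ask what happens to the result if dropouts did worse than the MMRM supposes. LOCF does not ask that. It replaces the missing Week 12 score with whatever was last recorded. For a subject who leaves with no off-drug visit, that is an on-drug score. The repeat-dose terminal half-life is "between 2.8 to 5.0 hours" (Protocol 1.5), and the plan gives no reason to expect an on-drug score to stand for weeks after stopping. Some subjects may leave for reasons unrelated to efficacy, since Protocol Appendix 11.2 requires discontinuation for confirmed laboratory abnormalities. They could leave with good scores.

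The plan also treats the same person in two ways. A dropout counts as a non-responder for IGA (SAP 7.1) but may keep a favourable last EASI under LOCF.

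At stake is how the key secondary result is read. If LOCF and MMRM agree, the report may call the effect robust to dropout, although no analysis has let dropouts lose the drug benefit.

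**Working it through.** **Inputs from the documents.** 250 randomized in five equal arms, 20% dropout, about 40 completers per arm (SAP 4.2.4): 40/(1 − 0.20) = 50 randomized per arm, so 10 of 50 per arm may lack Week 12 data. The documents give no EASI effect, SD or power, so there is no stated figure to reproduce for this endpoint. The 95% power refers to IGA.

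**1. What drives LOCF.** Let d be the fraction of an arm whose Week 12 value is carried. Let g be the mean carried score minus the mean Week 12 score those subjects would have under missing at random. Ignoring baseline adjustment,

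LOCF difference − MAR difference = d(active) × g(active) − d(placebo) × g(placebo).

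When the carried score is on-drug, g measures only how much improvement was still to come at exit. Nothing in it reflects what happens after the drug stops.

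**2. Illustration (all EASI inputs assumed).** SD 40, correlation between visits 0.8^lag, monotone dropout. Week 12 means are −60% drug and −35% placebo, a difference of −25; in the early-peak row the difference is −20. Negative values in the last column mean that LOCF looks better for the drug. Differences come from unrounded values.

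| Drug path; placebo path; dropout drug/placebo | MAR | LOCF | LOCF − MAR |
|---|---|---|---|
| Plateau by Week 4–6; gradual; random 20%/20% | −25.0 | −26.1 | −1.1 |
| Plateau by Week 4–6; gradual; random 10%/30% | −25.1 | −28.9 | −3.8 |
| Plateau by Week 4–6; gradual; lack of efficacy 20%/35% | −24.9 | −30.1 | −5.2 |
| Early peak, partial loss; gradual; random 20%/20% | −20.0 | −23.3 | −3.3 |
| Gradual; gradual; random 20%/20% | −25.0 | −22.2 | +2.9 |
| Gradual; flat; random 20%/20% | −25.1 | −20.2 | +4.9 |

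In the first row 0.2 × (g(active) − g(placebo)) = −1.1, so the gap in g is −5.5 points. In the fifth row it is 2.9/0.2 = +14.5 points. The dropout rule is identical; only the speed of drug onset differs.

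**3. Dropouts lose the benefit.** If random active dropouts take the placebo mean, the active mean is (1 − d) × μ(active) + d × μ(placebo), and the difference is (1 − d) × (μ(active) − μ(placebo)). With d = 0.20 this is 0.80 × (−25) = −20.0, a loss of 5 points or 20%. LOCF removed none of the effect in the first row. It happened to land close to −20 in the last row, because of the onset shape.

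**4. Which score is carried.** Subjects who stop treatment enter follow-up, with the first visit one week after the last dose (Protocol 6.4, Appendix 11.2). EASI is scored there (Protocol 6.3). The scheduled follow-up visits are 7, 14 and 28 days after Day 85. SAP Appendix 1 assigns efficacy data by relative day, with no on-treatment condition; Week 12 is Days 72–88. For a last dose on Day s:
- s + 28 lies in 72–88 for s = 44–60.
- s + 14 lies in 72–88 for s = 58–74.
- s + 7 lies in 72–88 for s = 65–81.

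So a subject who stops on about Days 44–81 and completes follow-up has an observed off-drug EASI in the Week 12 window, and nothing is carried. A subject who stops on Day 43 has visits near Days 50, 57 and 71, in the Week 6 and Week 8 windows (37–50 and 51–71). LOCF could then carry a score taken 28 days off drug. One week off drug is 168/5.0 = 33.6 to 168/2.8 = 60 half-lives. On-drug carry-forward is certain only for subjects with no off-drug visit.

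**The case against.** A reader might infer that LOCF will flatter the drug. The documents do not support that. Step 2 shows both signs. A second assumed set (−72% versus −30%, difference −42, SD 35, 50 per arm, 20% dropout) agrees. Random active dropouts combined with the worst placebo patients leaving gave LOCF of −41 to −48 across onset speeds. The same rule in both arms gave −36 to −42 (random) or −36 to −44 (worst patients leaving). A consistent advantage needs asymmetric dropout, which nothing in the plan establishes. At the lowest dose, active subjects may also leave for lack of efficacy.

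A reader might also infer that LOCF carries on-drug benefit for every dropout. The follow-up rules in step 4 contradict this. Nor does rescue fit that reading well: a subject who needs rescue is plausibly doing poorly, so the pre-rescue score need not be a good one.

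Plasma half-life is not EASI relapse time, and the documents give no relapse rate. The 20% shrinkage in step 3 restates the assumption that benefit is lost; it does not measure an error in LOCF.

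The stakes are also limited. This is Phase 2b, formal inference and multiplicity control cover only the primary endpoint (SAP 4.1, 4.2.2), and IGA uses non-responder imputation.

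All of this stands. It narrows the point but leaves the gap: no planned analysis tests the EASI result against loss of benefit in dropouts, and the SAP does not say which observation LOCF carries.

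**Conclusion.** The point holds in a limited form. ANCOVA with LOCF is the only planned analysis that varies missing at random for the key secondary endpoint. Because its departure from the MMRM follows onset shape and dropout pattern, agreement between the two would not show robustness at the planned 20% dropout, and disagreement would be hard to interpret.

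Direction and size cannot be settled from the documents. The illustrative contrast, a 20% loss of effect under placebo-like values against none under LOCF, rests on assumed means, SD, correlation, onset and random dropout. There is also a gap in definition: off-drug EASI can enter the Week 12 window as observed data or supply the carried value, and the SAP addresses neither case. The change should be made. The primary IGA analysis is not affected.

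**What to change.** 1. Keep the MMRM as primary.
2. In SAP 8.1.2 and 8.2.2.2.1, in place of LOCF or alongside it, add reference-based multiple imputation for percent change in EASI (for example jump to reference, combined by Rubin's rules) or a delta/tipping-point analysis.
3. Apply it only to values truly missing after discontinuation or set to missing after rescue. Do not overwrite EASI observed at off-drug follow-up visits.
4. In SAP 7.1, state whether LOCF carries the last on-treatment value or the last value of any kind. State also how off-drug EASI assigned to treatment-period windows by Appendix 1 enters the MMRM.
5. Reconcile the SAP 8.2.5 table with 8.2.2.2.1 by listing each sensitivity analysis that will be run.

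Return-to-baseline imputation alone is not a safe substitute. In the fast-plateau, gradual-placebo setting with 10%/30% random dropout it gave −29.5 against −25.1 under missing at random.

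The cost is SAP wording and a standard program, with no new data or visits. The sensitivity estimate will probably be less favourable than the MMRM.
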